7.1.12 Discontinuation of Study Treatment and Premature Subject Withdrawal

Subjects who discontinue prior to completing the 12-month or 18 month [¹⁸F]MK-6240 PET scan will be eligible for replacement in the study until a total of at least 15 MCI/AD subjects complete the 12 month PET imaging session. Subjects that complete the 12-month visit but wish to abandon the study before the 24-month visit will be given the option to have a final evaluation (including all the original assessments and imaging) any time between 18 and 24 months.

Subjects may voluntarily withdraw from the study for any reason at any time. They will be considered withdrawn if they state an intention to withdraw, fail to return for visits, or become lost to follow-up for any other reason.

If premature withdrawal occurs, the study team will make every effort to determine the primary reason for a subject's premature withdrawal from the study and document this information. In addition, the study team will ask the subject to return for an Early Terminations Visit for a final evaluation.

Subjects may develop adverse events or abnormalities in vital signs, physical or neurological examination, or laboratory determinations during their participation in the study. If these occur, the investigator may discontinue a subject from the study if, in his/her clinical judgment, continued participation would result in undue risk or further worsening of the condition.

For subjects who are lost to follow-up (i.e. those subjects whose status is unclear because they fail to appear for study visits without stating an intention to withdraw), the investigator will show due diligence by documenting attempts to contact the subject, e.g. dates of telephone calls, registered letters, or other attempts to communicate.

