STUDY DESIGN	
This is a longitudinal, observational study evaluating the imaging characteristics of the tau PET radioligand [¹⁸F]MK-6240 in AD, MCI and HV subjects. Up to 42 subjects including approximately 28 MCI/mild AD subjects, up to 5 moderate AD subjects, and 9 similarly aged HV subjects will be consented and screened. Imaging procedures include [¹¹C]PiB, [¹⁸F]MK-6240 PET and structural MRI.
 
All subjects who complete at least one [¹⁸F]MK-6240 PET imaging session will be considered enrolled in the study. As many as 28 MCI/mild AD subjects, 5 moderate AD subjects, and 9 similarly aged HV subjects may complete an evaluable baseline [¹⁸F]MK-6240 PET scan to enable at least 23 subjects (15 MCI/mild AD, 3 moderate AD, 5 HV subjects) to complete the 24 month follow up. Subjects who discontinue prior to completing the 12-month or 18-month [¹⁸F]MK-6240 PET scan may be replaced in the study until a total of 15 patients (MCI/AD) complete the 12 month PET imaging session. Subjects that complete the 12-month visit but wish to abandon the study before the 24-month visit will be given the option to have a final evaluation any time between 18 and 24 months.
 
All subjects will provide informed consent at enrollment before any study procedures are performed. The Screening procedures will occur within 60 days prior to baseline [¹⁸F]MK-6240 imaging and will include a brief cognitive

assessment, review of medical history and medications, physical examination, [¹¹C]PiB PET imaging and brain MRI.

[¹¹C]PiB and MRI IMAGING:

As part of the Screening Visit, subjects will complete structural brain MRI imaging which will be used for eligibility evaluation, co-registration with PET imaging and volumetric analysis.

If an evaluable PiB scan has been acquired and is available for use in this study and occurred within 12 months of screening, the scan will not be repeated. Otherwise, [¹¹C]PiB PET imaging will be obtained at screening to evaluate for amyloid deposition. Subjects will be considered amyloid positive if [¹¹C]PiB DVR (distribution volume ratio) imaging demonstrates amyloid deposition based on qualitative read or DVR index value >1.20.

For the [¹¹C]PIB PET imaging session, subjects will receive a single IV bolus injection target dose of 15 mCi ± 20% of [¹¹C]PIB and scanned dynamically for 70 minutes. For participants who may not be able to tolerate this long scan, a 20 minute scan will be offered after 50 minutes of uptake.

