10.4 Sample Size

The sample size for this study was determined by practical considerations and is not based on statistical power calculations. Up to 42 subjects maybe enroll in this study or no less than 15 MCI/mild AD subject, 3 moderate AD subjects and 5 similarly aged healthy volunteers all with a least the 12 month scan.

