1 PROTOCOL SYNOPSIS (FROM PROTOCOL)

TITLE	Longitudinal evaluation of [¹⁸ F]MK-6240 as a novel tau PET radiotracer in subjects with Alzheimer's disease or mild cognitive impairment compared to healthy volunteers
TEST PRODUCT	[¹⁸ F]MK-6240
STUDY CENTER	University of Wisconsin School of Medicine and Public Health
TRIAL OBJECTIVES	
The overall goal of this protocol is to characterize the longitudinal change in tau burden using [¹⁸F]MK-6240. Data from this study may be used to inform the design of future therapeutic trials utilizing [¹⁸F]MK-6240 as a marker of disease progression.
 
The primary objectives of this study are:
 
• To characterize the longitudinal change in [¹⁸F]MK-6240 brain uptake at 26 (6 months) and 52 (12 months) weeks compared to baseline in subjects with Alzheimer's disease (AD) dementia, mild cognitive impairment (MCI) and healthy volunteers (HV).• To correlate the changes in [¹⁸F]MK-6240 uptake and changes in clinical cognitive assessments (MMSE, ADAS-cog and CDR) 
The secondary objectives of this study are:
 
• To characterize the longitudinal change in [¹⁸F]MK-6240 brain uptake at 104 (24 months) weeks compared to baseline in subjects with AD dementia, MCI and healthy volunteers.• To evaluate cross-sectional comparison of [¹⁸F]MK-6240 uptake in AD, MCI and HV at baseline 26, 52 and 104 weeks

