STUDY DESIGN	
This is a longitudinal, observational study evaluating the imaging characteristics of the tau PET radioligand [¹⁸F]MK-6240 in AD, MCI and HV subjects. Up to 42 subjects including approximately 28 MCI/mild AD subjects, up to 5 moderate AD subjects, and 9 similarly aged HV subjects will be consented and screened. Imaging procedures include [¹¹C]PiB, [¹⁸F]MK-6240 PET and structural MRI.
 
All subjects who complete at least one [¹⁸F]MK-6240 PET imaging session will be considered enrolled in the study. As many as 28 MCI/mild AD subjects, 5 moderate AD subjects, and 9 similarly aged HV subjects may complete an evaluable baseline [¹⁸F]MK-6240 PET scan to enable at least 23 subjects (14 MCI/mild AD, 3 moderate AD, 6 HV subjects) to complete the 24 month follow up. Subjects who discontinue prior to completing the 12-month [¹⁸F]MK-6240 PET scan may be replaced in the study until a total of 15 patients (MCI/AD) complete the 12 month PET imaging session. Subjects that complete the 12-month visit but wish to abandon the study before the 24-month visit will be given the option to have a final evaluation any time between 18 and 24 months.
 
All subjects (or their legal authorized representative when applicable) will provide informed consent before any study procedures are performed. The Screening procedures will occur within 60 days prior to baseline [¹⁸F]MK-6240 imaging and will include a brief cognitive assessment, review of medical history and medications, physical examination, [¹¹C]PiB PET imaging and brain MRI.

--------------	---

[¹¹C]PiB and MRI IMAGING:

As part of the Screening Visit, subjects will complete structural brain MRI imaging which will be used for eligibility evaluation, co-registration with PET imaging and volumetric analysis.

If an evaluable PiB scan has been acquired and is available for use in this study and occurred within 12 months of screening, the scan will not be repeated. Otherwise, [¹¹C]PiB PET imaging will be obtained at screening to evaluate for amyloid deposition. Subjects will be considered amyloid positive if [¹¹C]PiB DVR (distribution volume ratio) imaging demonstrates amyloid deposition based on qualitative read or DVR index value >1.20.

For the [¹¹C]PiB PET imaging session, subjects will receive a single IV bolus injection target dose of 15 mCi ± 20% of [¹¹C]PiB and scanned dynamically for 70 minutes.

[¹⁸F]MK-6240 PET IMAGING VISITS:

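### Replacement ends at a pooled 15 MCI/AD patients, but the stated 12-month minimum is 18 patients counted by stage plus 5 volunteers; the 24-month target also differs between protocol and SAP

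*Protocol*

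**What the plan says.** **12-month minimum.** Protocol 10.4 and SAP 5.4 give the same figure: "no less than 15 MCI/mild AD subject, 3 moderate AD subjects and 5 similarly aged healthy volunteers", all with at least the 12-month scan. Both say the size rests on practical considerations and not on a power calculation.

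**Replacement rule.** It appears three times. Protocol 7.1.12 keeps discontinued subjects replaceable "until a total of at least 15 MCI/AD subjects complete the 12 month PET imaging session". The protocol synopsis and the SAP synopsis both say that such subjects "may be replaced in the study until a total of 15 patients (MCI/AD) complete the 12 month PET imaging session". None of the three separates the disease stages, and none counts volunteers.

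**Who can be replaced.** The protocol synopsis covers "Subjects who discontinue prior to completing the 12-month or 18-month" scan, and Protocol 7.1.12 agrees. The SAP synopsis names the 12-month scan only.

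**Caps and 24-month target.** The protocol synopsis allows over-enrolment: "As many as 28 MCI/mild AD subjects, 5 moderate AD subjects, and 9 similarly aged HV subjects may complete an evaluable baseline" scan, "to enable at least 23 subjects (15 MCI/mild AD, 3 moderate AD, 5 HV subjects) to complete the 24 month follow up". The SAP synopsis, whose heading says it comes from the protocol, has the same caps but "at least 23 subjects (14 MCI/mild AD, 3 moderate AD, 6 HV subjects) to complete the 24 month follow up".

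**The concern.** A replacement rule exists to protect the stated sample, so the two should count the same people. Here the sample-size sections count by stage and include volunteers, whereas the rule pools the stages and leaves volunteers out. Staff who follow the rule literally could stop replacing dropouts while the sample-size section is still unmet.

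This touches the main output. SAP 5.5 makes 12-month change the primary endpoint, and SAP 5.3 presents means and standard deviations by region and group as the project's primary objectives. Volunteers form their own group in every grouping the documents use, yet they have no replacement target. Whether a shortage of moderate AD completers would show in the primary output depends on a grouping the documents leave open: SAP 3.1 has AD, MCI and volunteers, while SAP 5.2 lists mild and moderate AD separately.

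**Working it through.** **Inputs.** Minimum 15/3/5 (Protocol 10.4, SAP 5.4); pooled trigger 15 (Protocol 7.1.12, both synopses); caps 28/5/9 (both synopses); 24-month targets 15/3/5 (protocol synopsis) and 14/3/6 (SAP synopsis). Triplets are MCI/mild AD, moderate AD, volunteers.

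**Stated totals.** All of them reproduce:
- Caps: 28 + 5 + 9 = 42.
- Protocol 24-month target: 15 + 3 + 5 = 23.
- SAP 24-month target: 14 + 3 + 6 = 23.

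The conflict is therefore between counts and not in the addition. The two 24-month splits share a total, so checking totals would not reveal the difference.

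**Minimum against trigger.** The 12-month minimum needs 15 + 3 = 18 patients, and the trigger stops at 15, a difference of 3 before stage is considered.

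**By stage.** Let b be the moderate AD completers, from 0 to the cap of 5, and a = T − b the MCI/mild AD completers when the pooled count is T. The shortfall against 15/3 is max(0, 15 − a) + max(0, 3 − b).

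| Pooled count T | b=0 | b=1 | b=2 | b=3 | b=4 | b=5 |
|---|---|---|---|---|---|---|
| 15 | 3 | 3 | 3 | 3 | 4 | 5 |
| 16 | 3 | 2 | 2 | 2 | 3 | 4 |
| 17 | 3 | 2 | 1 | 1 | 2 | 3 |
| 18 | 3 | 2 | 1 | 0 | 1 | 2 |

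At 15, no split meets 15/3. At 18, only 15/3 itself does. No modest increase in the pooled number cures this. With caps of 28 and 5, a pooled 30 could still be 28/2, so only 31 or more would ensure both stage minima. The trigger has to count by stage.

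**Volunteers.** They do not enter the count, so it can be satisfied with any number of volunteers scanned, including none.

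**24-month targets.** The patient part is 15 + 3 = 18 in the protocol and 14 + 3 = 17 in the SAP. Both exceed the pooled 15.

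**The case against.** The strongest reply is that replacement is not the main route to 15/3/5. The protocol synopsis provides over-enrolment up to 28/5/9 for that purpose. At a single non-randomised site, a replacement within the caps is in practice one more enrolment, and Protocol 7.1.12 does not close enrolment.

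Timing helps too. The trigger counts 12-month scans, due at 52 weeks ± 60 days, so it cannot be met earlier than 364 − 60 = 304 days after the last counted patient's baseline. Recruitment is planned for about 6 months (Protocol 5.2). Until the trigger is met, a lost subject from any group can be replaced, and when it is met others may still be on the way to their 12-month scan.

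Both arguments stand. A reader might infer from the table that the trial will finish 3 to 5 patients short. The documents do not support that, because the table describes the count when replacement may stop and not the final sample. It remains true that 28/5/9 are upper limits, not commitments, and nothing in the rule provides for replacement after the trigger is met.

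Three smaller replies:

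- *Protocol 7.1.12 sets a floor.* It does, but replaceability still runs only until that floor is reached.
- *MCI/AD was meant as MCI/mild AD.* Then the 3 moderate AD patients and 5 volunteers have no replacement target at all.
- *The SAP synopsis may simply lag the protocol.* That is plausible, since it omits the 18- and 30-month provisions throughout. It is still current text in the analysis plan and has to be reconciled.

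A reader might also see a contradiction within the SAP, with 6 volunteers at 24 months against a minimum of 5 at 12 months. That goes too far, because a minimum may be exceeded.

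**Conclusion.** The concern holds as a misalignment between the replacement rule and the stated minimum. Replacement may end at 15 pooled patients, when 15/3 is necessarily 3 to 5 patients short on the count at that moment and no volunteer number is secured. Whether a shortfall remains at the end depends on how far the caps are filled and how many subjects are still in follow-up, and the documents fix neither.

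The stage result assumes only that moderate AD completers number 0 to 5, the protocol's cap. A reader might infer a loss of power, but the size is not power-based and SAP 5.2 calls the analyses largely descriptive, so no power figure changes. The documents give no retention rate either. A probability of missing 15/3/5 would need assumed retention and enrolment and would mostly reflect the small caps, so it would not measure this defect.

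The differing 24-month splits and the missing 18-month wording in the SAP are separate, certain inconsistencies with a smaller consequence, since the SAP's analysis sections do not use either split. There is one further gap. Protocol 4.1 lets an 18-month measure stand in for a missing one, and the replacement rule mentions the 18-month scan, but its stopping count names only the 12-month session. It is unclear whether a substitute scan counts.

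**What to change.** Preferred: define the replacement trigger by group, as 15 MCI/mild AD, 3 moderate AD and 5 volunteers with the 12-month scan, within the existing caps of 28/5/9. Describe 15/3/5 as a target. The caps leave room to make good at most 5 − 3 = 2 moderate AD losses and 9 − 5 = 4 volunteer losses, so no replacement rule can guarantee it.

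Alternative: keep the pooled trigger, and say in Protocol 10.4 and SAP 5.4 that replacement secures only 15 pooled MCI/AD patients. Keep the moderate AD and volunteer numbers there as targets; do not delete them.

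With either option:
- use one 24-month split in both documents;
- reconcile the trigger wording between protocol and SAP;
- state whether a substitute 18-month scan counts toward the 12-month number.

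The cost is mainly wording in both documents. The first option may add a few replacement participants within the cap of 42, each with a screening visit and up to four planned MK-6240 scans. It still sets no number for MCI alone, because 15 pools MCI with mild AD. The second option costs a less favourable stated minimum.

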7.2 Study Completion

The study will be complete when the last subject (including replacement subjects) completes the final visit and follow up phone call.

7.3 Data Sharing:

Banked images and their meta-data from this study will be managed by the ADRC imaging core and provided to authorized ADRC and WRAP investigators. Images from ADRC participants may be uploaded to the National Alzheimer's Coordinating Center or other NIH-specified repository. The images from applicable subjects will also be shared back with the source protocols and with the ADRC UP protocol (2013-0178) to address the major specific aims of the UP project. Once the data are shared with repositories and with the source protocols, the data may be used to address future unspecified research by WRAP and ADRC investigators. Other investigators who wish to use these data may apply via established resource request mechanisms to the ADRC and WRAP, and the respective executive committees will evaluate the merit of the request and decide how these and other ADRC or WRAP data are shared. Investigators from within the ADRC and WRAP, other departments within UW, institutions outside UW, and private companies may submit applications requesting the data. Only coded data are shared with researchers that are not listed as key personnel on the projects. [name] holds ultimate responsibility for data sharing oversight, and will review all requests. He will ensure that local IRB policies are followed prior to releasing data.

Data shared with the study sponsor, Cerveau Technologies, Inc.:

Only data collected under this protocol will be shared with the study sponsor.

-MK-6240 Tau Brain PET Image

-Brain MR Images

- Unique Subject Identifier
- Amyloid image and status
- Cognitive metrics consisting of MMSE, ADAS-COG and CDR
- Weight/Height
- Scan time
- MK-6240 dose
- Scan date
- Clinical diagnosis
- Age, gender, race/ethnicity
- Smoking status

All data shared with Cerveau will be coded by participant ID. Cerveau maintains safety data for all sites using the MK6240 drug, and is responsible for Investigational Drug Brochure updates.

StatKing Clinical Services (TrialMaster)

The Electronic Data Capture (TrialMaster) will be hosted by StatKing Clinical Services, will be used to record all visit data. Data to be recorded include visit dates, dates of informed consent and enrollment, demography, health and smoking history, pregnancy test results if applicable, height/weight, APOE Status, vital signs, cognitive test scores, MRI sequence details, PET scan details, drug dosing details, AEs, concomitant medications, and follow-up call results. TrialMaster is in compliance with 21 CFR Part 11, electronic records, electronic signatures and predicate rules. Compliance is achieved through a combination of SOP adherence and a structured validation system. Security of the EDC system includes the use of passwords that limit user access according to their job responsibilities. Access to the data at the clinical site is restricted to authorized personnel only. Usernames and passwords are sent in two separate emails to personalized email addresses only.

BIOCLINICA

Bioclinica will provide secure storage of the study images and will be responsible for transferring MRI and PET images to the sponsor. Bioclinica will perform study start-up activities, prepare materials and forms which will be used for training and collection of images and perform image data quality control. Bioclinica will also prepare the study procedure manuals to ensure consistent image acquisition and transfer via SMART Submit, Bioclinica's electronic image submission system. SMART submit is in compliance with 21 CFR Part 11, electronic records, electronic signatures and predicate rules. Compliance is achieved through a combination of SOP adherence and a structured validation system. Security of this system includes the use of passwords that limit user access according to their job responsibilities. In addition, ongoing calibration of PET scanners will be monitored by the collection of quarterly report sheets. Throughout the study an image data back-up will be performed on data storage systems. Off-site image data back-up will also be performed. Other electronic data (electronic CRFs, audit trails, database contents, electronic documents, etc.) will be stored on a dedicated

database server and saved daily throughout the study. Access to the data at the clinical site is restricted to authorized personnel only.

7.4 Data Banking

Data banking is a required component of the study; participants must agree to data banking at the time of consent. Participants may request to have their data withdrawn from the bank, at which point study personnel will remove their data from the bank and will discontinue using it for further research. Data collected from this study will be stored on Department of Medicine computer servers that are password-protected. Banked data is coded with a subject ID. Only study personnel have access to the key linking subject ID and identifiable subject information. Unless staff are listed as key personnel on this study, they will not be given access to the code linking subject identity with subject ID.

8 SAFETY CONSIDERATIONS

8.1 Adverse Events

An **adverse event (AE)** is any unfavorable and unintended diagnosis, symptom, sign (including an abnormal laboratory finding), syndrome or disease which either occurs during the study, having been absent at baseline, or if present at baseline, appears to worsen. Adverse events will be recorded regardless of their relationship to the study.

A **serious adverse event (SAE)** is generally defined as any untoward medical occurrence that results in death, is life threatening, requires inpatient hospitalization or prolongation of existing hospitalization, results in persistent or significant disability/incapacity, or is a congenital anomaly.

Serious adverse events will be reported by the investigator to the Sponsor, FDA, and IRB within the required timeframes after learning of the event.

8.2 Adverse Events and Serious Adverse Events Monitoring

Given that this longitudinal study involves procedures that will occur at 6-12 month intervals and does not include chronic treatment with an investigational agent, adverse events (AEs) and serious adverse events (SAEs) will only be captured during the study visit before and after PiB and MK6240 scans. The participant will receive a phone call within 4 days from the study team for the purpose of ascertaining their wellbeing and information on any adverse events that occur within 24 hours after the scan. If any adverse events are discovered, a clinician will continue to follow up with the participant until resolved.

The PI will be apprised of any adverse events and will report any SAEs experienced in the study to the IRB, FDA and sponsor per the relevant regulations. Although no study related adverse events are expected (based on our past experience), we will examine AEs for study related trends. If needed, we would modify the consent form after consulting with the IRB.

8.3 Follow-up for Adverse Events

The investigator is obliged to follow subjects with AE's until the events have subsided, the conditions are considered medically stable, or the participants are no longer available for follow up. Subjects who discontinue due to adverse events will be treated and followed according to established medical practice.

